#### 10.3.3. Exploratory Analyses

PK, pharmacodynamics, and biomarker exploratory analyses will be described in the SAP finalized before database lock.

#### 10.3.3.1. Pharmacokinetic Analyses

Actual PK sampling date and times will be documented and the plasma concentration of IFX-1 will be assessed by time point. Summary statistics will be provided for the PK concentrations of

IFX-1 at all measured time points including also the geometric mean and its coefficient of variation. PK parameters including but not limited to  $C_{max}$  and  $C_{trough}$ , will be analyzed using descriptive statistics including also the geometric mean and its coefficient of variation.

#### 10.3.3.2. Immunogenicity Analyses

The number and percentage of patients with detectable ADAs against IFX-1 will be displayed per time point and overall post-baseline.

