- (8) FU every 3 months until 12 months after EOT Visit. All adverse events (AEs) with onset during treatment until EOT Visit will have to be followed until the outcome of the event is "recovering" (for chronic conditions) or until the end of study (EOS = last FU), and until all queries related to these AEs have been resolved. New related serious adverse events (SAEs) with onset during the follow up period (from the EOT Visit until the EOS) will have to be collected. FU visits may occur by telephone contact, if applicable.
- (9) 12-lead electrocardiogram (ECG): at screening, on C1D1 pre-dose and at H0+1 (±5 minutes), on C2D1 at H0+1 (±5 minutes), and at the EOT Visit
- (10) Hematology: red blood cells (RBC), white blood cells (WBC) with differential count, platelet count, hemoglobin, mean corpuscular volume (MCV) and hematocrit
- (11) Biochemistry: sodium, potassium, calcium, magnesium, alkaline phosphatase (ALP), total bilirubin, lactate dehydrogenase (LDH), aspartate aminotransferase (serum glutamic oxaloacetic transaminase (AST [SGOT]), alanine aminotransferase (serum glutamic pyruvic transaminase) (ALT [SGPT]), glucose, total proteins, albumin, urea, uric acid, creatinine, and C reactive protein (CRP).
- (12) Coagulation: activated partial thromboplastin time (aPTT), prothrombin time (PT).
- (13) Urine analysis: PH, glucose, leucocytes, proteins, blood.
- (14) Preferably Total T3, Free T4 should be analyzed, or other T3/T4 fractions (depending on local standards).
- (15) Pregnancy testing (WOCBP: women of childbearing potential only): During screening: serum beta-human chorionic gonadotropin test within 72 hours before first drug administration. During treatment period: urine pregnancy test. During FU urine pregnancy test on the first FU visit for Arm A, on the first FU visit and 120 days after the last dose of pembrolizumab for Arm B
- (16) Complement: C5a to be performed at pre-dose during treatment period. C3a to be performed only at C1D1 [pre-dose]
- (17) Antidrug antibodies (ADAs) against IFX-1 to be performed at pre-dose during treatment period.
- (18) Pharmacokinetics: To be performed at pre-dose during treatment period and in addition at the end of infusion H0+0.5h (-5/+10 minutes, but not before the end of IFX-1 administration) on Cycle 1 Days 1 and 22.

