# 4.2.2. Secondary Endpoints

# 4.2.2.1. Monotherapy Arm A

Secondary endpoints comprise the following:

- Response (CR/iCR/PR/iPR) and stable disease (SD) duration
- Disease control rate (CR/iCR+PR/iPR+SD)
- PFS
- OS
- Frequency, severity, and IND attribution of treatment-emergent AEs (TEAEs) and SAEs according to MedDRA coding (version valid at time of reporting) and the National Cancer Institute common terminology criteria for AEs (NCI CTCAE) grading system (version 5.0, 27 November 2017)
- Post infusion ( $C_{max}$ ) and trough concentration ( $C_{trough}$ ) of IFX-1
- Development of human ADAs against IFX-1
- Changes in QoL as per the European Organisation for Research and Treatment of Cancer (EORTC)-QoL questionnaire (QLQ)-C30 total score

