# **8.1.** Baseline Assessments

The following procedures will be performed to assess baseline characteristics during screening evaluations and before study treatment administration:

- Documentation of demographic details (age, gender, race, and ethnicity), medical and disease history (see Sections 8.1.1 and 8.1.2)
- Disease assessments (see Section 8.2 and Appendix 3)
- QoL/EORTC (see Section 8.8)
- Documentation of concomitant disease and prior and concomitant medications (see Sections 8.1.3 and 8.1.4)
- Baseline safety assessment (height, weight, physical exam, vital signs, electrocardiogram (ECG), AEs, and safety laboratory; see Section 8.3)
- Skin or metastasis biopsy (if skin biopsy is not possible) for biomarker assessments (see Section 8.6)
- Baseline assessment of pharmacodynamic parameters (C3a, C5a, ADA) and PK

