# **10.3.** Statistical Analyses

The statistical analysis plan (SAP) will be developed and finalized before the first patient is enrolled. The SAP will include the exact definition of endpoints and variables to be analyzed, extensive details on the statistical analysis methods to be used together with the structure of tables and figures to be included as end-of-text tables and figures as well as appended listings for the clinical study report. It will also describe procedures for accounting for missing, unused, and spurious data. This section is a summary of the planned statistical analyses of the primary and secondary endpoints.

Individual data will be listed. Data will be summarized using suitable descriptive statistics; depending on the structure of the data, summary statistics (e.g., number of observations, mean, standard deviation, minimum, median, maximum, lower quartile, upper quartile) or frequency tables may be used.

All data will be displayed by treatment arm if not specified otherwise.

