## 10.3.2. Safety Analyses

All safety analyses will be performed on the SAS.

An AE is considered as treatment emergent if it starts during or after first administration of study treatment (IFX-1 or pembrolizumab). The number and percentage of patients with TEAEs, SAEs, and AESIs for IFX-1 and/or pembrolizumab will be analyzed, as well as the number of TEAEs, SAEs, and AESIs with the respective MedDRA System Organ Class and Preferred Term. Where AEs are grouped by NCI CTCAE grade or relationship, the maximum grade/relationship per patient and class of AE will be considered. The described analyses will be performed for the treatment period and the follow-up period separately. AEs reported during screening or before first study treatment administration will be categorized as pre-treatment AEs.

Safety laboratory, vital signs, and 12-lead ECG parameters will be analyzed by summary statistics (e.g., number of observations, mean, standard deviation, minimum, median, maximum, lower quartile, upper quartile) for absolute values and changes from baseline by visit. Shift tables comparing baseline and the worst post-baseline assessment will be prepared if applicable.

Categorical safety parameters, like findings from physical examination, will be summarized by absolute and relative frequencies by time point.

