# 10.3.3.3. Quality of Life Analyses

QoL will be assessed by the EORTC-QLQ-C30. The change from baseline of the total score will be analyzed descriptively at each measured time point as a secondary endpoint.

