  - Vital signs (Cycle 1 Days 1 [pre- and post-dose], 4, 8, 15, 22 and 36; Days 1, 15, and 29 of each cycle from Cycle 2 on until EOT Visit)
  - AEs (Cycle 1 Days 1 [pre- and post-dose], 4, 8, 15, 22 and 36; Days 1, 15, and 29 of each cycle from Cycle 2 on until EOT Visit)
  - ECG (Cycle 1 Day 1 [pre- and post-dose], Cycle 2 Day 1 [post-dose])
- Blood and urine samples for safety laboratory:
  - Hematology (Cycle 1 Days 1 [pre-dose], 8, 15, 22, and 36; Cycle 2 Days 1, 15, and 29;
     and Day 1 of each subsequent cycle onwards until EOT Visit)

- Biochemistry (Cycle 1 Days 1 [pre-dose], 8, 15, 22, and 36; Cycle 2 Days 1, 15, and 29;
   and Day 1 of each subsequent cycle onwards until EOT Visit)
- Coagulation parameters (Cycle 1 Day 1 [pre-dose], Cycle 2 Day 1)
- Urinalysis (Cycle 1 Days 1 [pre-dose], 8, 15, 22, and 36; Cycle 2 Days 1, 15, and 29; and Day 1 of each subsequent cycle onwards until EOT Visit)
- Thyroid stimulating hormone, preferably total T3, free T4 (or other T3/T4 fractions depending on local standards) (Cycle 1 Day 8, and Day 1 of each subsequent cycle until EOT Visit)
- Urine pregnancy test (WOCBP) (Cycle 1 Days 8, 22, and 36; Days 1, 15, and 29 in Cycle 2 and each subsequent cycle until EOT Visit)
- Plasma and serum sampling pre-dose:
  - C3a at Cycle 1 Day 1 [pre-dose]
  - C5a in plasma (Cycle 1 Days 1 [pre-dose], 8, 15, 36 and 22; Day 1 of Cycles 2, 3, 5, and then of every other cycle until EOT Visit)
  - ADAs against IFX-1 in serum (Cycle 1 Days 1 [pre-dose] 15, 22 and 36; Day 1 of Cycles 2, 3, 5, and then of every other cycle until EOT Visit)
- PK parameter assessment:
  - At pre-dose on Cycle 1 Days 1, 8, 15, 22, and 36; Day 1 of Cycles 2, 3, 5, and then of every other cycle until EOT Visit
  - Additionally, post dose H0+0.5h (-5/+10 minutes, but not before the end of IFX-1 administration), or just after the end of administration in case of decrease in infusion rate on Cycle 1 Days 1 and 22
- Tumor biomarkers
  - Skin biopsy (Screening, and for Stage 2 patients only: Cycle 2 Day 1 (mandatory), once at time of CR/iCR/PR/iPR (optional), and/or at PD (optional)
  - If skin biopsy is not possible: Metastasis biopsy (Screening, and for Stage 2 patients only: Cycle 2 Day 1, once at time of CR/iCR/PR/iPR, and/or at PD (optional)

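### The ADA summary counts any detectable ADA after baseline and ignores the pre-dose sample, so it can overstate the endpoint, which is the development of ADAs

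*Combined protocol and SAP*

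**What the plan says.** Section 4.2.2.1 lists "Development of human ADAs against IFX-1" as a secondary endpoint for Arm A, and Section 4.2.2.2 lists the same endpoint for Arm B.

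The only analysis of it is in Section 10.3.3.2: "The number and percentage of patients with detectable ADAs against IFX-1 will be displayed per time point and overall post-baseline". That section does not condition on baseline status, state a denominator, or separate new from pre-existing or boosted ADA.

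A baseline sample is planned. Section 8.1 includes "Baseline assessment of pharmacodynamic parameters (C3a, C5a, ADA) and PK". Appendix 1 (Treatment Visits) schedules "ADAs against IFX-1 in serum (Cycle 1 Days 1 [pre-dose] 15, 22 and 36", with further samples in later cycles. Table 1 marks ADA sampling as mandatory, and its footnote reads "Antidrug antibodies (ADAs) against IFX-1 to be performed at pre-dose during treatment period". The Day 1 sample is therefore a true pre-exposure value.

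Elsewhere the plan does relate results to the start of treatment. Section 10.3.2 states "An AE is considered as treatment emergent if it starts during or after first administration of study treatment" and puts earlier events in a pre-treatment category. Section 10.3.3.3 states for quality of life: "The change from baseline of the total score will be analyzed descriptively at each measured time point as a secondary endpoint". ADA has no equivalent rule.

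**The concern.** Development means a change after exposure: the patient lacked detectable antibodies before IFX-1 and has them afterwards. The overall summary measures something else, namely detection at any time after baseline. The two agree only if nobody has detectable reactivity before the first dose. If some do, a stable pre-existing positive enters the numerator and is read as a response to the drug.

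What is at stake is how the immunogenicity result is interpreted. Section 8.3 lists ADA status as a safety assessment, and Section 3.3 discusses anti-IFX-1 antibodies as a potential risk. In an arm of about 29 patients one reclassified patient moves the percentage visibly, and the reported figure may later be set beside ADA rates from other IFX-1 studies.

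**Working it through.** **Plan's own figure.** The documents state no ADA rate for this trial, the ADA range from earlier studies is redacted, and no prevalence before the first dose is given. There is nothing to reproduce. The one number taken from the plan is the sample size of 29 per arm (Section 10.1: 10 in Stage 1 plus 19 in Stage 2).

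**Notation.** N = patients with a baseline and at least one post-baseline sample; b = patients positive at Cycle 1 Day 1 pre-dose; t = patients negative then and positive later. Assume first that all b baseline positives are detectable again later.

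- Rate as written: (b + t)/N
- Treatment-emergent rate: t/(N − b)
- Difference: b(N − b − t)/[N(N − b)], which is zero when b = 0 and never negative under this assumption

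**Illustration with N = 29 and t = 2 (b and t are assumed).**

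| b | As written | Treatment-emergent | Gap (points) |
|---|---|---|---|
| 0 | 2/29 = 6.9% | 2/29 = 6.9% | 0 |
| 1 | 3/29 = 10.3% | 2/28 = 7.1% | 3.2 |
| 2 | 4/29 = 13.8% | 2/27 = 7.4% | 6.4 |
| 3 | 5/29 = 17.2% | 2/26 = 7.7% | 9.5 |

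**If the baseline positive does not persist.** With b = 1 and no detection afterwards, the written rule gives 2/29 = 6.9% against 2/28 = 7.1%, which is practically no difference. Only persistent positives matter.

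**Chance that the issue arises.** With assumed baseline prevalence q, the probability of at least one baseline positive among 29 is 1 − (1 − q)^29: 25% at q = 1%, 44% at 2%, 77% at 5% and 95% at 10%. None of these values of q comes from the documents.

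**Other denominators.** Each persistent baseline positive adds 1/N to the rate as written: 1/29 = 3.4 points. The weight is 1/10 = 10.0 points if Arm A stops after Stage 1. It is 1/41 = 2.4 points if all of the up to 41 Arm B patients in Section 10.1 are included.

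**The case against.** **The definition is deferred.** Section 10.3 is a summary and promises that "The SAP will include the exact definition of endpoints and variables to be analyzed". Section 8.3.6 leaves assay and analysis methods to a Bioanalytical Protocol. Neither supplies an ADA definition in the text at hand, and a later SAP could still define treatment-emergent ADA. This is a fair point, but Section 10.3.3.2 is not silent. It states a rule, and that rule does not match the endpoint. The SAP therefore needs to be told to depart from it.

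**Baseline positives will be visible.** The per-time-point display should include Cycle 1 Day 1 pre-dose, and Section 10.3 says that individual data will be listed. This stands: a careful reader could rebuild the treatment-emergent rate from the listings. The summary figure itself would still be uncorrected.

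**Overall post-baseline prevalence is a legitimate summary.** The objective is to monitor immunogenicity, and dropping that count would remove patients whose pre-existing ADA rises on treatment. This also stands, and is why the new summary should be added and the existing one kept.

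**Stronger readings.** A reader might infer that the reported rate will be inflated, or inflated by a particular amount. The documents do not support that. They give no baseline prevalence, and even at an assumed 3% the chance of no baseline positive among 29 is 0.97^29 = 41%. A reader might also infer that analyses of ADA against trough levels, C5a or infusion reactions would be diluted. No such analyses are specified. Section 3.3 describes few human ADA cases so far, but with the rate redacted this does not show that one or two baseline positives would dominate the result.

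**Conclusion.** The point holds in conditional form. The stated ADA summary measures detection after baseline, while the endpoint in both arms is development, and the mandatory pre-dose result that separates the two is not used in the overall figure. The figure can overstate drug-induced ADA.

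The bias is zero if no patient is positive before the first dose. Otherwise its size depends on how many are positive and stay detectable, which the documents do not allow anyone to estimate. The gaps of 3.2 and 9.5 points for one and three persistent positives assume 29 sampled patients, 2 new positives and full persistence. Comparing with 2/29 would give 3.4 and 10.3 points, but 2/29 is not the rate among patients who could newly develop ADA.

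The endpoint is secondary and descriptive, with no test or decision attached. The response-rate decision, its error rates and the dose-escalation rules are unaffected. The change is worth making because it is cheap and uses data already planned.

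**What to change.** In Section 10.3.3.2 and the SAP:

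- Keep the per-time-point display, stating that it includes Cycle 1 Day 1 pre-dose, and keep the overall post-baseline prevalence under that name.
- Add, as the summary for the development endpoint, the number and percentage with treatment-emergent ADA. The numerator is patients negative at Cycle 1 Day 1 pre-dose with at least one positive sample afterwards. The denominator is baseline-negative patients with at least one post-baseline sample.
- Report baseline-positive patients separately, as unchanged or boosted where the assay gives a titre, with the titre-rise criterion fixed in advance.
- State the denominator for each arm, including whether Arm B counts the run-in patients.

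The cost is a few lines of text, one extra table row and a slightly smaller denominator. No new samples or visits are needed. If titre is not available, baseline-positive patients can only be listed as such, and keeping the overall prevalence ensures that they are not lost from view.

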# 10.3.3.3. Quality of Life Analyses

QoL will be assessed by the EORTC-QLQ-C30. The change from baseline of the total score will be analyzed descriptively at each measured time point as a secondary endpoint.

## 10.3.3.4. Pharmacodynamic Analyses

Pharmacodynamics endpoints will be analyzed using descriptive statistics.

## 10.3.4. Interim Analyses

#### 10.3.4.1. Formal Interim Analysis Based on Simon's 2-Stage Design

An interim analysis based on Simon's 2-stage design (Simon, 1989) of treatment response will be performed after Stage 1 in both treatment arms (monotherapy Arm A and combination therapy Arm B) before enrollment into Stage 2.

The interim analysis will be performed on the first 10 patients evaluable for the Phase II portion per arm when these 10 patients have performed their third post-baseline tumor assessment OR discontinued treatment. At the time of the interim analysis, a treatment arm will be discontinued if 0 responders are observed in the respective treatment arm. A responder is defined as in Section 10.3.1. Each treatment arm will be evaluated separately such that it may occur that enrollment into both arms is stopped, enrollment into 1 arm is stopped and the other is continued to the second stage, or enrollment into both arms is continued. If both arms are discontinued after Stage 1, the final analysis will be performed after all patients enrolled in Stage 1 will have completed or discontinued the study and described in a clinical study report. If enrollment is stopped, patients will still receive treatment until disease progression (EOT), or are discontinued due to other reasons, and will then be followed up for 12 months.

## 10.3.4.2. Safety Run-In Based on 3+3 Design (Combination Therapy Arm B)

The safety run-in phase in the combination Arm B will follow a 3+3 design for escalation of the IFX-1 treatment regimen based on the following escalation rules:

• If 0 of 3 patients experience a DLT during the DLT observation period (see Section 7.2.2.2.3) at a certain IFX-1 treatment regimen, the subsequent 3 patients will be enrolled in the next higher IFX-1 treatment regimen.

- If 1 of 3 patients experience a DLT, another 3 patients will be enrolled at the same IFX-1 treatment regimen.
  - If 1 of 6 patients (i.e., none of the subsequent 3 patients) experiences a DLT, the combination arm will escalate to the next IFX-1 treatment regimen.
  - If ≥1 of 6 patients at the same IFX-1 treatment regimen experience a DLT, this treatment regimen will be stopped.
- If >1 of 3 patients at the same IFX-1 treatment regimen experience a DLT, this treatment regimen will be stopped.
- If a treatment regimen is stopped, the next lower treatment regimen is considered as MTD.
- In the highest IFX-1 treatment regimen (regimen 3): if ≤1 of 6 patients experience a DLT, this will be determined as RP2D.
- 6 patients will need to be treated at the MTD or at the highest IFX-1 dose level (Regimen 3, if MTD was not reached) to decide if this dose can be selected as RP2D which will then be explored in the Phase II portion of Arm B. In case only 3 patients will have been previously treated at the MTD or highest IFX-1 dose level, 3 more patients will be added to this cohort. If 6 patients were already treated at the proposed dose level, then additional patients will not be required and the decision on the RP2D will be made based on the available data.
- The subsequent patients will be enrolled at the RP2D to fill up the first stage of the Simon's 2-stage design for the combination arm (4 additional patients to reach the required sample size of 10).

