# 5.2.2. Combination Therapy Arm B

# **5.2.2.1. Safety Run-In**

After  $\geq 3$  patients have been treated in Arm A under close monitoring by the steering committee, the safety run-in of Stage 1 of treatment Arm B will be opened. Patients will be sequentially enrolled into 3 escalating dose cohorts and their safety will be monitored by the steering committee, as described in Section 5.3.2.

The safety run-in part will follow a 3+3 design as described in 10.3.4.2 and monitored by the steering committee: 3 patients will be enrolled in the lowest dose cohort (IFX-1 regimen 1 + pembrolizumab). If 1 of the 3 patients experiences a DLT (see Section 7.2.2.2.3), the cohort will be expanded to a total of 6 patients. If  $\geq 1$  patient of 3 or > 1 patient of 6 develop a DLT, further dose escalation is not pursued, and the next lower dose will be chosen as the MTD (see Section 7.2.2.2.4). If there is no DLT observed in any of the first 3 patients, or in only 1 of 6 patients, 3 new patients will be enrolled in the next higher dose cohort (IFX-1 regimen 2 + pembrolizumab). For the second and third dose cohort (IFX-1 regimen 3 + pembrolizumab), the same rules apply. If the MTD is not reached, the highest dose (IFX-1 regimen 3 + pembrolizumab) will be chosen as potential RP2D (see Section 7.2.2.2.4). 6 patients will have to be treated at the highest IFX-1 or MTD dose level to confirm the respective dose to be used in Stage 2. In case only 3 patients will have been previously treated at the MTD or highest IFX-1 dose level, 3 more patients will be added to this cohort. If 6 patients were already treated at the proposed dose level, then additional patients will not be required and the decision on the RP2D will be made based on the available data. When the MTD or RP2D has been established, Stage 1 of Arm B will continue with the Phase II portion (see Section 5.2.2.2).

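### As extracted, Section 10.3.4.2 both escalates and stops an expanded run-in cohort at 1 DLT in 6, and Section 5.2.2.1 has a similar slip at 1 in 3; other text states the intended rule

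*Combined protocol and SAP*

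**What the plan says.** Section 5.2.2.1 introduces the run-in with "The safety run-in part will follow a 3+3 design as described in 10.3.4.2", so Section 10.3.4.2 is where the escalation rules are set out.

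Section 10.3.4.2 handles 1 DLT in the first 3 patients by enrolling 3 more at the same regimen. Two sub-bullets follow under that case. The first covers 1 of 6 and reads in part "i.e., none of the subsequent 3 patients) experiences a DLT, the combination arm will escalate to the next IFX-1 treatment regimen". The second reads "If ≥1 of 6 patients at the same IFX-1 treatment regimen experience a DLT, this treatment regimen will be stopped".

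Three further bullets stand outside that nesting:
- for the first three patients, "If >1 of 3 patients at the same IFX-1 treatment regimen experience a DLT, this treatment regimen will be stopped"
- for the consequence of stopping, "If a treatment regimen is stopped, the next lower treatment regimen is considered as MTD"
- for the top dose, "In the highest IFX-1 treatment regimen (regimen 3): if ≤1 of 6 patients experience a DLT, this will be determined as RP2D"

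Section 5.2.2.1 says that after 1 DLT in 3 "the cohort will be expanded to a total of 6 patients". Its next sentence begins with the sign ≥1 and continues "patient of 3 or > 1 patient of 6 develop a DLT, further dose escalation is not pursued". That sentence refers to Section 7.2.2.2.4 for the MTD. Section 7.2.2.2.4 places the MTD one level below the regimen stopped for more than 1 DLT in a cohort of 3 or more than 1 in an expanded cohort of 6. Section 5.2.2.1 also escalates when only 1 of 6 patients has a DLT.

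**The concern.** A cohort expanded after 1 of 3 already contains one DLT. If it is stopped at 1 or more of 6, no expanded cohort can ever pass, and enrolling the second 3 patients serves no purpose. Read literally, a cohort with 1 of 3 followed by 0 of 3 gets two opposite instructions from adjacent lines: escalate, and stop. At regimen 3 the same result makes that regimen the RP2D and also makes regimen 2 the MTD.

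The run-in fixes the dose for the Arm B Phase II portion. Regimen 3 carries 1600 mg Q2W, which Section 3.2.5.1 names as the target dose. What is at stake is stopping below that dose by mistake, or a steering committee dispute over wording just after a DLT has occurred.

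The slip in Section 5.2.2.1 is of the same kind: 1 of 3 both expands the cohort and ends escalation.

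**Working it through.** **The rules side by side, as extracted**

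| DLTs | 10.3.4.2 | 5.2.2.1 | 7.2.2.2.4 |
|---|---|---|---|
| 0 of 3 | escalate | escalate | no stop |
| 1 of 3 | expand | expand, **and** end escalation (≥1 of 3) | no stop |
| >1 of 3 | stop | end escalation | stop |
| 1 of 6, after 1 of 3 | escalate (RP2D at regimen 3), **and** stop (≥1 of 6) | escalate | no stop |
| >1 of 6 | stop | end escalation | stop |

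Only the two bold entries disagree with the rest. Section 10.3.4.2 has the 1-of-3 case right, Section 5.2.2.1 has the 1-of-6 case right, and Section 7.2.2.2.4 has both right.

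**How often the 1-of-6 conflict would arise**

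The plan states no operating characteristic for the run-in, so there is no figure to reproduce. It gives no DLT rate either. I assume a rate q of 10%, 20% or 30%, the same at all three regimens. The calculation concerns the 10.3.4.2 line only, since 5.2.2.1 defers to 10.3.4.2, where the 1-of-3 case is correct.

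Because the disputed line sits under the 1-of-3 case, it conflicts only on the path 1 of 3 then 0 of 3. The path 0 of 3 then 1 of 3 at regimen 3 falls under the separate RP2D bullet, without conflict.

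- 0 of 3: A = (1−q)³ = 0.729, 0.512, 0.343
- 1 of 3 then 0 of 3: B = 3q(1−q)² × (1−q)³ = 0.1771, 0.1966, 0.1513

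Conflict per regimen entered = B = **17.7%, 19.7%, 15.1%**.

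At least one conflict in the run-in: the first conflict comes at regimen 1, or at regimen 2 after one 0-of-3 cohort, or at regimen 3 after two. So P = B(1 + A + A²):
- q = 10%: 0.1771 × 2.2604 = **40.0%**
- q = 20%: 0.1966 × 1.7741 = **34.9%**
- q = 30%: 0.1513 × 1.4606 = **22.1%**

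**Effect on the chosen dose if the stop line were obeyed**

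Regimen 3 needs 6 patients. P(0 of 6) = A², and the paths 1 of 3 then 0 of 3 and 0 of 3 then 1 of 3 each have probability B. Hence P(at most 1 of 6) = A² + 2B = 0.8857, 0.6554, 0.4202.

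- Intended rule: P(regimen 3 chosen) = (A + B)² × (A² + 2B)
  - 0.9061² × 0.8857 = **72.7%**
  - 0.7086² × 0.6554 = **32.9%**
  - 0.4943² × 0.4202 = **10.3%**
- Stop line obeyed: the B path is lost at every regimen, giving A² × (A² + B)
  - 0.5314 × 0.7086 = **37.7%**
  - 0.2621 × 0.4588 = **12.0%**
  - 0.1176 × 0.2689 = **3.2%**

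The Simon figures in Section 10.1 (early termination 59.9%, type I error 4.7%, type II error 19.9%) reproduce with exact binomials and do not depend on this wording.

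**The case against.** The strongest reply is that the documents already answer the question. Section 5.2.2.1 gives the >1-of-6 rule in its stopping sentence, and that sentence points to Section 7.2.2.2.4, which states it again. Within Section 10.3.4.2, the sub-bullet just before the disputed line takes exactly 1 of 6, so the next one makes sense only as the remainder. A committee with at least 3 cSCC experts is unlikely to read it otherwise. All of this stands. It makes the point a wording correction and makes the literal-reading probabilities an upper bound.

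A second reply is that the sign may be a reading artefact. Neighbouring counts in Section 10.3.4.2 are underlined, and an underlined > can be read as ≥. Signs also differ for the same criterion elsewhere: radiation washout (synopsis against Section 6.1) and the irAE grade in exclusion criterion 5 (synopsis against Section 6.2). This stands as a caveat. It is not decisive, because both signs appear close together in Section 10.3.4.2 and within one sentence of Section 5.2.2.1, so not every > became ≥.

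In the other direction, a reader might infer that the stop line governs every 6-patient cohort, including 0 of 3 then 1 of 3 at regimen 3. That would double the conflict probability at regimen 3, to 35.4%, 39.3% and 30.3%. The nesting under the 1-of-3 case does not support it.

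**Conclusion.** The point holds as a minor correction, provided the source PDF shows the signs as extracted. If it shows >1 in either clause, the point falls for that clause.

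Two stopping thresholds in a live dose-selection rule are wrong as written. A reader might infer that the plan leaves 1 of 6 unresolved, or that patients face added toxic exposure. Neither is supported. The intended rule is stated outright in Sections 5.2.2.1 and 7.2.2.2.4, and the literal error stops too early rather than too late.

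The disputed result is not rare: about 15% to 20% per regimen entered at the assumed rates. A wrong decision is much less likely, because it also requires the committee to follow the one dissenting line. The figures rest on assumed DLT rates, taken as equal across regimens. No sample size, alpha or power figure changes.

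**What to change.** Check both signs in the source PDF first. If they read as extracted:

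- Section 10.3.4.2, second sub-bullet under 1 of 3: change ≥1 of 6 to >1 of 6.
- Section 5.2.2.1, stopping sentence: change ≥1 patient of 3 to >1 patient of 3.
- Optional, Section 5.3.2: the dose is selected there on condition that no further toxicities are seen. Replace that condition with at most 1 of the 6 patients having a DLT.

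All sections then agree with 7.2.2.2.4: 0 of 3 escalate; 1 of 3 expand; more than 1 of 3 stop; 1 of 6 escalate, or RP2D at regimen 3; more than 1 of 6 stop. The cost is two signs and one optional phrase, with no added patients, time or procedures.
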